| Quality of Recovery                                     |                             |           | X         | X                   | X                     | X                     | X                      |                                   |
| TRUS  | X                           | X         |           |                     | X                     |                       |                        |                                   |
| Concomitant Medication                                  | X                           | X         | X         | X                   | X                     | X                     | X                      | X                     |
| Adverse events  |                             | X         | X         | X                   | X                     | X                     | X                      | X                     |

Basic metabolic profile

Required for patients who are sexually active 4 weeks prior to the questionnaire completion date

Only urological SAEs and urological adverse event related medication and all BPH medication

Only urological SAEs and urological adverse events

**Medical history:** During the baseline assessment, the investigator or coordinator will record details of medical history as they relate to BPH.

**Serum Blood Test:** A blood sample should be collected prior to the surgical procedure to measure PSA, complete blood count (CBC), and Basic Metabolic Panel (BMP) to include at least levels of creatinine, sodium, and blood urea nitrogen. A CBC and BMP should also be collected following the first voiding trial and prior to discharge. PSA will also be repeated at 6 months, 12 months, 24 months, 36 months, 48 months, and 60 months follow-up visit.

**Uroflowmetry:** Uroflowmetry test is performed at baseline, 1 month, 3 months, 6 months, 12 months, 24 months, 36 months, 48 months, and 60 months follow-up visit. For Qmax to be valid for a patient, the total voided volume must be  $\geq 125\text{mL}$ . If the total voided volume is less than 125mL, the voided volume must be equal to or greater than 50% of the bladder capacity (defined as voided volume + PVR). The patient can repeat the test if necessary.

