**Incontinence Severity Index:** ISI is a validated means of assessing incontinence and will assist in isolating *de novo* incontinence rather than pre-existing incontinence secondary to Bladder Outlet Obstruction (BOO). This questionnaire will be completed at baseline, 1 month, 3 months, 6 months and 12 months follow-up visit.

**International Prostate Symptom Score (IPSS):** IPSS is a validated measure of urinary dysfunction due to BPH. This questionnaire will be completed at baseline, 1 month, 3 months, 6 months, 12 months, 24 months, 36 months, 48 months, and 60 months visit.

**Pain Severity Assessment (NRS) and Dysuria Score:** NRS and Dysuria Scores are a method of measuring post-operative pain and pain on micturition. This questionnaire will be completed at baseline, 1 month, 3 months and 6 months follow-up visit.

**International Index of Erectile Function Questionnaire (IIEF-15):** IIEF-15 is a validated, fifteen-item questionnaire designed to diagnose the presence and severity of erectile dysfunction. This questionnaire will be completed at baseline, 1 month, 3 months, 6 months, and 12 months follow-up visit. IIEF-5 is a subset of IIEF-15 that has also been validated for the measurement of erectile function.

**Male Sexual Health Questionnaire to assess Ejaculatory Dysfunction (MSHQ-EjD):** MSHQ-EjD is a validated, four-item questionnaire that assesses ejaculatory function and related distress or bother. This questionnaire will be completed at baseline, 1 month, 3 months, 6 months, and 12 months follow-up visit.

**Quality of Recovery.** This is a validated visual analog scale rating of quality of recovery from surgery. The scale extends from “poor recovery” to “excellent recovery.”

**Transrectal ultrasound (TRUS):** TRUS will be performed to assess eligibility for prostate volume, length, transverse width, anterior/posterior width, and general condition of the prostate. Presence of a middle or intravesical lobe should be documented by sagittal images. TRUS will be conducted at baseline, treatment, and 3 months follow-up visit.

**Concomitant Medications:** The following will be recorded on a rolling log: BPH medication, post-operative pain medication, all AE related medications up to the 12 months visit, and all urological SAE and urological AE related medications for the 24 months, 36 months, 48 months, and 60 months visits.

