#### **4.2 Per-protocol (PP) Cohort**

The per-protocol (PP) population is all mITT subjects who:

1. meet critical study eligibility criteria;
2. have no significant protocol deviations that could affect the validity of data; and
3. have evaluable assessment for the endpoint of interest.

A significant protocol deviation means non-adherence on the part of the subject or investigator to clinically significant protocol-specific inclusion/exclusion criteria, primary objective variable criteria or critical study requirements that could affect the scientific validity of the observed data point or lead to bias. Missing data are not imputed for analyses with the PP cohort.

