#### **4.3 Safety Cohort**

The safety analysis population includes all subjects in whom Aquablation is initiated. This cohort is used for most safety analyses.

---

\* See <https://cran.r-project.org/>

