## **5 STUDY ENDPOINTS**

### **5.1 Primary Effectiveness Endpoint**

The primary effectiveness endpoint is the IPSS change score from baseline to 3 months. IPSS is an accepted and commonly used measure for symptom severity in BPH. IPSS varies from 0 (no symptoms) to 35 (maximal symptoms). The mean 3-month IPSS change score (abbreviated dIPSS3) in WATER was 16 points (SD=7 points). WATER used a non-inferiority margin of 5 points; 5 points represents the minimum change for men with moderate-to-severe BPH that is detectable. The current study's goal is therefore to show that the IPSS change score statistically exceeds 16-5 = 11 points. The study's hypotheses are therefore:

$$\begin{aligned} H_0: \text{dIPSS}_3 &\leq 11 \\ H_a: \text{dIPSS}_3 &> 11 \end{aligned}$$

A one-way t test with the mITT cohort will be used for the calculation. With 100 patients and assuming 10% subjects lost to follow, 90 evaluable subjects with an underlying change of 16 points and a change score SD of 7.5 points yields a 99% power to detect an improvement of more than 11 points.

A secondary goal is to show similarity of change scores between WATER II and WATER. Data from WATER and WATER II will be combined. Regression analyses controlling for baseline IPSS score (a strong predictor of change scores) will calculate differences in change scores between WATER and WATER II subjects. WATER II will be determined to have similar dIPSS3 scores if the 95% confidence limits for the difference between WATER and WATER II Aquablation subjects exceeds -5 points. The study is not necessarily powered for this comparison.

Missing data for dIPSS3 will be imputed using the following rules:

- Predicted value from baseline IPSS: In WATER, dIPSS3 was strongly and statistically significantly related to baseline IPSS (Figure 1). This finding is not surprising for maximally effective procedures that reduce scores to close to maximal (i.e., a ceiling effect). A linear regression model using WATER II available data will be used to predict missing change scores.
- Low value: A change score of 0 points
- High value: a change of 5 less than the maximal possible improvement, which represents change scores from WATER (see also Figure 1)

[figure not shown]

Figure 1. Relationship between baseline IPSS and 3-month change score in WATER. Blue = Aquablation, red = TURP.

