## **6.6 Change in MSHQ-EjD**

Mean change from baseline in MSHQ-EjD score at 3 months. Preservation of ejaculatory function is defined as a change non-inferior to -4 points. (Note that there is no published minimally clinically important difference for MSHQ-EjD.) A t test with 95% confidence intervals will be used to evaluate this hypothesis. If non-inferiority is concluded, a secondary test will calculate whether the change score represents statistical superiority.

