## **6.7 Change in IIEF-5**

Mean change from baseline in IIEF-5 (aka SHIM, part of IIEF-15) at 3 months. Preservation of erectile function, meaning a change score non-inferior to -6 points. An approach similar to that listed for MSHQ-EjD will be used.

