## **7 ADDITIONAL ENDPOINT ASSESSMENTS**

Additional exploratory statistical analysis will be done using standard statistical methods. Analyses of interest are:

1. Proportion/rate of all Clavien-Dindo classifications at month 3.
2. Changes in the following ratings across all time points: IPSS, IPSS-QOL, Incontinence Severity Index (ISI), IIEF-15, MSHQ-EjD, pelvic pain intensity score, dysuria frequency and intensity score, and uroflow measures. For this and other repeated assessments, repeated measures analysis of variance may be used to calculate change from baseline. Semi-quantitative comparisons will be made to results from WATER.
3. Relationship between baseline IPSS and IPSS change scores.
4. Duration of bladder catheterization.
5. Whether discharged home with a bladder catheter.
6. Change in hemoglobin from preoperative to postoperative. Additional analysis will be performed to see if prostate size, anesthesia type, number of Aquablation passes, and intravesical median lobes were predictors of bleeding loss.
7. Reoperation rate at 1 year for lack of efficacy. (This endpoint excludes reoperation for complications.)
8. Change in proportion of subjects using BPH medications (e.g., alpha blockers, alpha-reductase inhibitors).
9. Prostate size reduction from baseline to 3 months as measured TRUS. A t test will be used for the comparison.
10. Relationship between prostate size and procedure or resection times. Linear or other models will be used to explore relationships.
11. Proportion of subjects with device- or procedure-related adverse event.
12. Proportion of subjects in whom re-catheterization was needed between discharge after the index procedure and month 3. Re-catheterization is defined as the need to place a urinary catheter in the bladder for symptoms related to BPH (primarily inability to urinate). This excludes re-catheterization for study purposes or for purposes unrelated to LUTS.
13. Amount of irrigation fluid used intraoperatively (liters). A t test or Wilcoxon's test will be used to compare to values from WATER.

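### Month-3 IIEF-15 and MSHQ-EjD scores are required only of men who are still sexually active, and SAP 6.6 and 6.7 state neither the analysis set nor the handling of men scored only at baseline

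*Protocol*

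**What the plan says.** **Who is scored.** In Protocol 2.19, the sexual-function row of Table 2 covers baseline and months 1, 3, 6 and 12. Its footnote 2 reads "Required for patients who are sexually active 4 weeks prior to the questionnaire completion date". The condition is tied to each completion date, so it is applied again after treatment. The IIEF-15 and MSHQ-EjD paragraphs under the table give the same visits without repeating the condition.

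**How the scores are tested.** Protocol 3.3 lists both change scores among the secondary endpoints for marketing claims. SAP 6.6 sets a margin of -4 points for MSHQ-EjD and says "A t test with 95% confidence intervals will be used to evaluate this hypothesis"; a superiority test follows if non-inferiority is concluded. SAP 6.7 has "Preservation of erectile function, meaning a change score non-inferior to -6 points" and borrows the 6.6 approach. Neither section names a cohort, says at which visit a man must be sexually active, or mentions a missing month-3 score.

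**Missing data elsewhere.** The rules introduced by "will be imputed using the following rules" in SAP 5.1 are for the 3-month IPSS change only. SAP 4.2 says "Missing data are not imputed for analyses with the PP cohort", but 6.6 and 6.7 do not invoke that cohort. SAP 4.1 names mITT as the primary population for the two primary endpoints. SAP 4.3 says of the Safety cohort "This cohort is used for most safety analyses" and gives no missing-score rule. SAP 7 offers that "repeated measures analysis of variance may be used to calculate change from baseline", as an exploratory option.

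**Dysfunction proportion.** Protocol 3.3 counts erectile or ejaculatory dysfunction at 3 months in men sexually active at baseline, with no relatedness condition. SAP 6.2 counts only events that the CEC rates as possibly, probably or definitely related. It then adds further calculations that leave out subjects whose event is judged unrelated.

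**The concern.** Having a month-3 score is itself a post-treatment outcome. A man who was active at baseline and stopped because his function declined need not be scored at month 3. If the t test uses available pairs, which is the natural default when no rule is given, he drops out and the remaining men look better preserved.

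The route is most direct for erectile loss, which Protocol 2.20 defines by whether an erection suffices for satisfactory sexual activity. Ejaculatory loss is defined as absent seminal emission. That need not end activity, so many men with it would still be scored.

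At stake are two non-inferiority conclusions intended for marketing claims. On the minor point, the reported dysfunction rate may be lower than the one the protocol defines.

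**Working it through.** The documents give no sample size, power, SD or expected number of active men for these two endpoints, so there is no stated figure to reproduce. The calculation below asks only whether the gap could matter.

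**Inputs from the documents:** margins -4 and -6; two-sided 95% interval (SAP 6.6, 6.7).

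**Assumptions:** n = 75 baseline-active men; 8, 15 or 23 of them unscored at month 3; scored SD 4 (MSHQ-EjD) or 5 (IIEF-5); unscored SD 2.

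**Formulas** (s = scored, u = unscored):
- M = (n_s·m_s + n_u·m_u)/n
- S² = [(n_s-1)·SD_s² + (n_u-1)·SD_u² + n_s·(m_s-M)² + n_u·(m_u-M)²]/(n-1)
- Lower limit = M - t(0.975, n-1)·S/√n, with t = 1.9925 for n = 75

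**Worked case, MSHQ-EjD, 60 scored at -1.5 and 15 unscored at -10:**
- Scored men only: -1.5 - 2.001 × 4/√60 = -2.53, which passes.
- All 75: M = (-90 - 150)/75 = -3.20.
- Within-group sum of squares: 59 × 16 + 14 × 4 = 1000. Between-group: 60 × 1.7² + 15 × 6.8² = 867.
- S = √(1867/74) = 5.02. Lower limit = -3.20 - 1.9925 × 5.02/8.66 = -4.36, which fails.

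**Other MSHQ-EjD cases (margin -4):**

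| Scored mean | Unscored mean | 15 unscored | 8 unscored |
|---|---|---|---|
| -0.5 | -10 | -3.62, holds | -2.63, holds |
| -1.5 | -10 | -4.36, fails | -3.48, holds |
| -2.5 | -6 | -4.11, fails | -3.79, holds |

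**IIEF-5 (margin -6), unscored men averaging -10:**

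| Scored mean | 15 unscored | 23 unscored |
|---|---|---|
| -1 | -4.14, holds | -5.14, holds |
| -2 | -4.88, holds | -5.76, holds |
| -3 | -5.63, holds | -6.39, fails |

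**Tipping points** (mean change in unscored men that puts the lower limit on the margin):

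| Unscored of 75 | MSHQ-EjD, scored mean -0.5 / -1.5 / -2.5 | IIEF-5, scored mean -1 / -2 / -3 |
|---|---|---|
| 8 | -18.6 / -13.4 / -7.6 | -27.4 / -22.4 / -17.1 |
| 15 | -11.4 / -8.6 / -5.5 | -16.9 / -14.3 / -11.5 |
| 23 | -8.2 / -6.5 / -4.7 | -12.2 / -10.6 / -9.0 |

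**Checks:**
- If unscored men resemble scored men (mean -1.5, SD 4), the limit for all 75 is -2.41 and there is no bias.
- With other assumptions (70 men, 14 unscored, SD 5 in both groups, means -2 and -10), the lower limit moves from -3.34 to -5.01. MSHQ-EjD reverses and IIEF-5 holds.
- In that second model, with SD 4 to 6, IIEF-5 fails only once 30% to 40% are unscored.

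**Minor point, SAP 6.2.** A man whose only event is rated Unrelated or Unlikely is not counted, which lowers the reported rate by 1/75 = 1.3 points (1/50 = 2.0; 1/90 = 1.1). A man who also has a related event is still counted.

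**The case against.** A reader might infer that footnote 2 and the 2.19 text contradict each other on who completes the questionnaires. The documents do not support that. The text lists visits and never says all subjects, and Protocol 2.13 and 2.18 both refer to Table 2 for the detailed tests and requirements. This is a restriction that the text does not repeat. The gap in the SAP remains, because the footnote is then the operative rule.

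The mechanism and the arithmetic also point to different instruments. Selective drop-out is most plausible for erectile loss, yet IIEF-5 is the more robust test; the reversals come more easily for MSHQ-EjD, where the route is weaker. Even the erectile route is inferred. Being sexually active is not defined, so a man with dysfunction may still count as active and be scored, and footnote 2 does not bar scoring inactive men. The documents give no score ranges, so whether the larger drops are attainable has to be checked. All of this limits the size of the concern but does not supply the missing rule.

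Harm is bounded. Protocol 2.20 records adverse events in all men to 12 months. An affected man can still appear in the dysfunction proportion and, if the loss is persistent and probably or definitely related, in the primary safety endpoint.

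On SAP 6.2, one might argue that the further calculations make sense only if the first calculation covers all events. That does not follow: the sentence excludes subjects, so it may shrink the denominator. For illustration, 10 men with related events and 3 with only unrelated events among 75 give 10/75 = 13.3%, then 10/72 = 13.9%. Protocol 6.1 also gives the filter some support by having CEC adjudication govern related events in the secondary safety analysis, although it does not limit the 3.3 proportion to them.

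**Conclusion.** The concern holds in limited form. Month-3 scoring depends on post-treatment sexual activity, and SAP 6.6 and 6.7 define neither the analysis set nor the handling of men scored only at baseline. Any selective loss of men with reduced function would favour preservation.

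The size is unknown. It is zero if men stop for reasons unrelated to function or if sites score everyone. Under the stated assumptions, the MSHQ-EjD conclusion can reverse with 15 of 75 men unscored when the scored mean is -1.5 or lower. The reversals shown at 15 do not occur with 8, although a scored mean of -2.5 leaves little room even then (tipping point -7.6). With unscored men averaging -10, IIEF-5 reverses only at about 23 of 75 unscored and a scored mean near -3.

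It would go too far to say that the preservation results are biased or invalid; the documents show only that the plan leaves this open. The SAP 6.2 difference is real but minor, since that endpoint carries no hypothesis and the all-event rate can be recovered from recorded adverse events. The primary effectiveness test is untouched. The point should be fixed because these endpoints are meant for marketing claims and the remedy is cheap.

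**What to change.** - **Protocol 2.19:** repeat the footnote 2 condition in the IIEF-15 and MSHQ-EjD paragraphs.
- **SAP 6.6 and 6.7:** define the analysis set as men sexually active at baseline, as Protocol 3.3 already does for the dysfunction proportion, and state how a missing month-3 score is handled.
- **Any remaining month-3 visits:** seek a score or the reason for inactivity from that whole set, after checking that the instruments score inactive men validly.
- **Reporting:** give the number of baseline-active men unscored at month 3, the reasons, and how many have an erectile or ejaculatory adverse event.
- **Sensitivity:** add a tipping-point analysis for the unscored men. Use lowest-score imputation only as an extreme bound, because it overstates loss in men who stopped for other reasons.
- **SAP 6.2:** report the protocol's all-event proportion first and the CEC-related proportion second, on the same denominator. State whether the further calculations remove subjects from the denominator.

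The cost is some SAP wording, one listing and one sensitivity analysis, using data already planned. Protocol 2.11 describes 101 men already treated, so completed month-3 visits cannot be repaired; for those, only the reporting and the sensitivity analysis apply. The downside is that the preservation results may look less favourable.

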## **2.20 Adverse events**

The occurrence of all adverse events will be documented in all study subjects throughout the study treatment and 12 months follow-up period. Only urological SAEs and urological events will be collected at 24 months, 36 months, 48 months, and 60 months follow-up visits. AE information (start and stop date, description of event, severity, relatedness to the treatment procedure, the device itself or other study-related procedures) will be assessed and recorded on CRFs. Whether an AE meets the definition for serious adverse event will be determined by the study investigator using **Table 3**. All urological events consistent with a SAE must be reported to the Sponsor within 24 hours of awareness of the event. Relatedness of the AE to the surgical procedure or the study device itself will be judged by the clinical events committee (CEC) for adverse events up to 12 months according to **Table 4**.

The classification of surgical complications shall be done per **Table 5** by the CEC. Note that persistent ejaculatory or erectile dysfunction, the need for re-catheterization after postoperative day 3, and urinary incontinence related to surgery are considered to be surgical complications.

**Table 3 Adverse Event Definitions**

| Term                                       | Definition   |
|--|--|
| Adverse event* (AE)                        | Any untoward medical occurrence in a subject.  |
| Serious adverse event* (SAE)               | 
An adverse event that:
 
 
led to a death,
 
led to a serious deterioration in the health of the subject that 
 
resulted in a life-threatening illness or injury,
 
resulted in a permanent impairment of a body structure or a body function,
 
required hospitalization or prolongation of existing hospitalization,
 
resulted in medical or surgical intervention to prevent permanent impairment to body structure or function,
 
led to fetal distress, fetal death, a congenital abnormality, or birth defect.
 
 
 
 |
| Adverse device effect (ADE)                | Any untoward and unintended response to a medical device. This term includes any event resulting from insufficiencies or inadequacies in the instructions for use or the deployment of the device or any event resulting from user error.  |
| Serious adverse device effect (SADE)       | An adverse device effect that has resulted in any of the consequences characteristic of a serious adverse event or that might have led to any of these consequences if suitable action had not been taken or intervention had not been made or if circumstances had been less opportune.   |
| Unanticipated Adverse Device Effect (UADE) | Any serious adverse effect on health or safety or any life-threatening problem or death caused by, or associated with, a device, if that effect, problem, or death was not previously identified in nature, severity, or degree of incidence in the investigational plan or application (including a supplementary plan or application), or any other unanticipated serious problem associated with a device that relates to the rights, safety, or welfare of subjects.   |

\*Note that these definitions do not imply a relationship between the adverse event and the AQUABEAM System.

**Non-Reportable Events** - Mild to moderate symptoms that are typically associated with the usual post-operative course including but not limited to dysuria, decreased urinary flow, gross hematuria within 7 days post treatment.

**Ejaculatory dysfunction** – The absence of seminal emission

**Erectile dysfunction** – The inability to achieve and maintain an erection sufficient for satisfactory sexual activity

**Urinary Retention** – Subjects with an episode of the inability to urinate without the use of a catheter

**Urinary Retention Adverse Event** – Subjects who present beyond 7 days post-index treatment and are unable to void requiring catheterization to resolve their symptoms

**Urinary Incontinence** – Subjects who didn't require incontinence pads prior to Aquablation treatment and require 1 or more incontinence pads per day post-index treatment.

